The QFT-GIT assay has limitations as a test for *Mtb* infection, due to intra-subject and dynamic variability around the diagnostic threshold recommended by the manufacturer and by the US Centers For Disease Control And Prevention (CDC) (0.35 IU/mL) (Pai, 2012; Mazurek et al, 2010). In a study of short-term serial QFT-GIT testing in South Africa, QFT-GIT assays were associated with a 4% false positive conversion rate, supporting the recommendation that an “uncertainty zone” of 0.2 – 0.7 IU/mL (i.e., increasing the positive threshold value) be applied to interpretation of QFT-GIT results (van Zyl-Smit et al, 2009). QFT-GIT assay variability appears maximal in low burden settings with low rates of TB infection. Repeat testing of individual QFT-GIT samples in a low burden setting showed that the normal expected range of within-subject variability is  $\pm 0.24$  IU/mL (coefficient of variation 27%) for individuals with a QFT-GIT response within this “uncertainty zone” (Metcalf et al, 2013). Serial QFT-GIT testing of Canadian health care workers, with expected TST conversion rates of less than 1%, has also shown unexpectedly high QFT-GIT conversion rates (5%) unrelated to occupational TB exposure risk (Zwerling et al, 2013). These unexpected QFT-GIT conversions were associated with a high rate of spontaneous reversion (62%).

Findings from high TB burden settings with high risk of *Mtb* infection, such as South Africa, where the rate of QFT-GIT conversion is similar to the expected rate of TST conversion, are in contrast to the pattern observed in serial testing of low risk study populations, where the rate of QFT-GIT conversion has been unexpectedly high compared to TST (Pai, 2012; Zwerling et al, 2013). For example, in South African adolescents, the QFT-GIT assay performs equally as well as the TST for prediction of subsequent active TB disease (Mahomed et al, 2011b). In a high risk South African community, the QFT-GIT conversion rate among QFT-GIT baseline negative adolescents was less than the rate of TST conversion (5mm threshold) over the same period (17% vs. 24%) (*unpublished SATVI data*). These preliminary data indicate that QFT-GIT conversion is an appropriate endpoint to define *Mtb* infection, and vaccine-induced prevention of *Mtb* infection, for clinical trials among South African adolescents.

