### 7.3 Prevention of Infection (QFT-GIT Conversion) Analyses

The primary *Mtb* infection endpoint will be QFT-GIT conversion from a negative to positive test, using the manufacturer's recommended threshold of 0.35 IU/mL, at any time-point after Day 84 and through end of follow-up for the primary endpoint (see below). The frequency of QFT-GIT negativity/positivity will be summarized for each treatment group at screening, on Day 84, on Month 6, and for all subsequent assessments. The log-rank statistic will be used to test the null hypothesis of no difference in the rates of *Mtb* infection over the follow-up period between each of the AERAS-404 and BCG groups compared to the placebo group. The log-rank test statistic compares estimates of the hazard functions of the vaccine groups at each observed event time. It is constructed by computing the observed and expected number of events in the groups at each observed event time and then summing these to obtain an overall summary across all time points where there is an event. As subjects convert their QFT-GIT tests over time (experience a primary endpoint) or are lost to follow up the number of subjects at risk over time will change. As this is a proof of concept study, these two log-rank tests (AERAS-404 compared to placebo and BCG revaccination compared to placebo) will be performed with a 1-sided Type 1 error of 0.1. There will be no adjustment for multiplicity to control the Type 1 error rate over the two tests. The rationale for not performing this adjustment is related to the fact that the tests pertain to efficacy assessments of two unrelated vaccines. If these two evaluations were performed in two separate trials then no adjustment for multiplicity would be made. Thus, one should not be compelled to adjust for this multiplicity simply because the two evaluations are performed administratively in a single trial.

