## 7.6 Sample Size Considerations

Sample size for the trial is based on the power to detect a reduction in the rate of infection with *Mtb*, as determined by QFT-GIT conversion. As a proof of concept study looking for evidence of biologic impact, the trial is designed to distinguish a QFT-GIT conversion rate reduction of 50% compared to placebo for each vaccine (AERAS-404 and BCG) with power of 80% and a type 1 error rate of 10% (1-sided).

Trial design calculations are performed by computer simulation. The simulations estimate the statistical operating characteristic of a conditional binomial test which, due to relative rarity of the endpoint, provides an excellent approximation to the operating characteristic of the log-rank tests which will be used in the analyses of trial data. The following assumptions, based on preliminary data from SATVI (Mahomed et al, 2011b) were used in these simulations:

- Primary *Mtb* infection endpoint rate = 10% per year
- Rate of loss to follow up = 7% per year
- Average rate of enrollment = 20 subjects per week
- Maximum duration of follow up to primary conversion = 24 months with 6-monthly study visits

Under these assumptions, a total sample size of 990 is expected to provide 64 primary QFT-GIT conversion endpoints approximately 21 months after the first subject is enrolled. Follow up will continue until 64 endpoints are accrued and a median follow up duration of 15 months for individual subjects have both occurred. A 10% rate of QFT-GIT conversions per year is conservative (SATVI data have shown an average 17% conversion rate in adolescents); however, continuing to follow subjects until the required number of endpoints is accrued ensures adequate power for the primary endpoint.

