## 7. STATISTICAL CONSIDERATIONS

### 7.1. ADJUSTMENTS FOR COVARIATES AND FACTORS TO BE INCLUDED IN ANALYSES

Not applicable.

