  - o For the sensitivity analysis the following SAS code will be implemented:

```
PROC LIFETEST DATA = <> METHOD=lt INTERVALS=(0 to 2 by 0.5)
PLOTS=(s) ;
TIME Years*Censored(1) ;
FREQ count;
RUN;
```

- Vaccine efficacy is derived as:
  - o  $VE = 1 - \text{Hazard Rate Ratio (Vaccine/comparator)}$
  - o The hazard ratio is estimated based on the following Cox regression model:

```
PROC PHREG DATA = <>;
MODEL Time to Event (Months) * Censor (1) = Treatment Group;
RUN;
```

- Censor = 1 represents censored participant.
    - Censor = 0 represents participant who experienced an event.
    - Months represent the available follow-up time (months) per participant since randomization.
  - o The 80% CI is based on the two-sided hazard ratio confidence interval and will be derived as:
    - $VE_{\text{lower limit}} = 1 - \text{Hazard ratio}_{\text{upper limit}}$
    - $VE_{\text{upper limit}} = 1 - \text{Hazard ratio}_{\text{lower limit}}$
  - o The 95% CI is based on the two-sided hazard ratio confidence interval.

- For the sensitivity analysis, interval censoring will be used based on the following code:

```
PROC ICPHREG DATA = <>;
MODEL (left, right) = Treatment Group /b=pch(NINTERVAL=X);
RUN;
```

- Left represents left censoring value in months.
  - Right represents right censoring value in months.
  - Left and right censoring values are dependent on where the event is identified:

Visit at Which Primary Event Identified	Left Censoring Value	Right Censoring Value
M6	3	6
M12	6	12
M18	12	18
M24	18	24

Document: Aeras\_C-040-404\_SAP\_V2\_0

Author: [name]

Version Number:

2.0

Version Date:

29SEP2017

Template No: CS\_TP\_BS016 – Revision 3

Reference: CS\_WI\_BS005

Effective Date: 01May2012

Copyright © 2012 Quintiles Transnational Corp. All rights reserved.

The contents of this document are confidential and proprietary to Quintiles Transnational Corp. Unauthorized use, disclosure or reproduction is strictly prohibited.

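### The final analysis makes no use of the quantitative screening QFT-GIT value; a supportive adjusted analysis and one baseline table row would guard against chance imbalance, though they would not narrow the confidence interval

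*SAP*

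**What the plan says.** SAP 7.1, headed "ADJUSTMENTS FOR COVARIATES AND FACTORS TO BE INCLUDED IN ANALYSES", answers that the item does not apply. The primary Cox model in SAP 14.1.3 is "MODEL Time to Event (Months) * Censor (1) = Treatment Group", and the secondary model in SAP 14.2.3 has the same single term. The log-rank tests in SAP 14.1.2 and 14.2.2 are unstratified. Protocol 7.3 makes the log-rank the test and says the two comparisons "will be performed with a 1-sided Type 1 error of 0.1".

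Protocol Tables 3-1 and 3-2 schedule QFT-GIT at screening for every participant. SAP 14.1.2 lists Nil, Ag and Mitogen in IU/mL as collected, and SAP 14.3.2 plots change from baseline after conversion, so the baseline value will be in the analysis data. SAP 10 does not list it among baseline characteristics. The by-visit table in SAP 14.1.2 gives only negative, positive or missing, and everyone eligible is negative at screening. Only the individual listing shows the level.

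Protocol 1.1 names as a limitation of the assay its "intra-subject and dynamic variability around the diagnostic threshold recommended by the manufacturer", 0.35 IU/mL, and cites an uncertainty zone of 0.2 to 0.7 IU/mL.

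**The concern.** The endpoint is a crossing of a cut-off on a continuous assay. A participant who screens just under 0.35 IU/mL has less far to go than one who screens near zero, so the screening level probably predicts conversion. The SAP recognises this elsewhere: one of its alternative definitions asks for a value below 0.2 before conversion and above 0.70 at conversion.

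If the arms happen to differ in the share of borderline screeners, the unadjusted hazard ratio moves with that difference, and no planned summary would reveal it. The trial is small in events and tests two vaccines at one-sided 0.10 without multiplicity control, so a modest shift could matter to a decision on further development.

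**Working it through.** **1. The design figure.** Protocol 7.6 says "the trial is designed to distinguish a QFT-GIT conversion rate reduction of 50% compared to placebo for each vaccine", at 80% power and one-sided 0.10, and that 990 participants "is expected to provide 64 primary QFT-GIT conversion endpoints approximately 21 months after the first subject is enrolled".
- Events needed per pair (Schoenfeld): 4(1.2816 + 0.8416)² / (ln 0.5)² = 37.5, so 38.
- With one vaccine active, 64 events split 1 : 0.5 : 1. The placebo-vaccine pair has 64 × 1.5/2.5 = 38.4.
- Power = Φ(√38.4 × 0.6931/2 − 1.2816) = Φ(0.866) = 80.7%. The plan's figure reproduces.

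**2. Precision.** The 38.4 events are 25.6 on placebo and 12.8 on vaccine. SE of the log hazard ratio ≈ √(1/25.6 + 1/12.8) = 0.342. Simulated Cox models (2,000 trials per setting, 330 per arm) gave an SE of about 0.34 with and without the baseline term. At HR 0.5 the 80% interval is 0.5 × exp(±1.2816 × 0.342) = 0.32 to 0.78, so VE 22% to 68%, either way. The SE is set by the event counts; adjustment moves the log hazard ratio by only 0.00 to 0.03.

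**3. Power.** The documents give neither the screening distribution nor its link to conversion. Both are therefore assumptions, shown as ranges.

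Log-rank at true HR 0.5, 3,000 simulated trials per row:

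| Share at 0.20-0.34 IU/mL | Conversion rate vs the rest | Unstratified | Stratified |
|---|---|---|---|
| 10% | 3× | 80.7% | 80.8% |
| 10% | 5× | 77.8% | 79.2% |
| 20% | 5× | 78.5% | 80.1% |
| 10% | 10× | 74.8% | 78.7% |

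Cox model at true HR 0.5, unadjusted to adjusted:
- Continuous predictor, log-HR per SD of 0.3, 0.5 and 0.8: 79.0% to 78.9%, 79.1% to 79.6%, 77.0% to 78.7%.
- Binary predictor, 5% share at 5×, 10% at 5× and 10% at 8×: 78.2% to 78.6%, 79.0% to 80.9%, 77.8% to 79.7%.

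Each power has a simulation error of about √(0.79 × 0.21/3000) = 0.7 points (0.9 with 2,000 trials).

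**4. Chance imbalance under no effect.** With share f and rate multiple h, the SD of the between-arm difference in share is √(2f(1−f)/330). For f = 10% this is 2.34 points. A one-SD difference d in the vaccine's favour shifts the log hazard ratio by about s = ln{[1+(h−1)(f+d/2)] / [1+(h−1)(f−d/2)]}. With no effect, a pair has 64 × 2/3 = 42.7 events, so SE = √(4/42.7) = 0.306. Put q = s/0.306. Given that imbalance, the rejection rate is about Φ[(−1.2816 + q)/√(1−q²)].

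| f, h | s | q | By formula | Simulated |
|---|---|---|---|---|
| 10%, 3× | 0.039 | 0.127 | 12.2% | – |
| 10%, 5× | 0.067 | 0.218 | 13.8% | 13.5% |
| 20%, 5× | 0.069 | 0.226 | 13.9% | 13.8% |
| 10%, 10× | 0.111 | 0.362 | 16.2% | 16.2% |

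A weak continuous predictor (0.3 per SD) gives s = 0.3 × √(2/330) = 0.023, q = 0.076 and 11.3%. Across all checks the range is about 11% to 17%. Stratifying on the borderline zone held the rate at about 9% to 11%. Averaged over all randomizations it is close to 10% with or without stratification.

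**5. Secondary endpoint.** With 20% reversion there are 64 × 0.8 = 51.2 events, or 51.2 × 1.5/2.5 = 30.7 per pair. Power is 71% (Freedman) to 74% (Schoenfeld), against the protocol's 70%. No adjusted simulation was run for this endpoint.

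**The case against.** The case for leaving the plan alone is strong in four respects.

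- **Validity.** The unadjusted log-rank is valid over repeated randomizations, and its interval already allows for chance imbalance. This stands. A reader might infer from step 4 that the planned test has an inflated type I error; it does not. The 11-17% applies only given an unfavourable draw.
- **Precision.** A reader might infer that omitting a predictor widens the interval. Step 2 shows otherwise. Adjustment in a Cox model also targets a slightly different, conditional hazard ratio.
- **What the protocol says about the assay.** It would be tempting to read Protocol 1.1 as saying that results near 0.35 IU/mL convert through assay variation alone. It does not. It places the largest variability in low-burden settings, takes its ±0.24 IU/mL figure from one, and concludes that conversion is an appropriate endpoint in South African adolescents. The 4% false-conversion rate it cites is South African, but it is not linked to baseline level.
- **Existing safeguards.** The modified intent-to-treat set requires a second negative test at Day 84. The secondary endpoint needs three consecutive positives, and the <0.2 to >0.70 definition has its own efficacy tables. These target dilution of efficacy by false conversions, which a baseline covariate would not remove.

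None of this makes an imbalance visible. Nor does randomization alone guarantee balance in the modified intent-to-treat set, because membership depends on a test taken after vaccination that borderline screeners are the likeliest to fail.

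**Conclusion.** The omission is real and the consequence is small to moderate. Using the screening value would leave the confidence interval as wide as it is, add about 0 to 4 points of power (mostly 0 to 2; the 4 needs a tenfold conversion rate), and protect against a chance imbalance that could take the conditional type I error from 10% to about 11-17%. These figures assume that 5-20% of participants are borderline and convert at 3 to 10 times the rate of the rest, or an equivalent continuous gradient; the documents confirm neither.

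The documents do not support replacing the primary test. Protocol 7.3 names the unadjusted log-rank, and SAP 4.2 records that the event-driven primary analysis is already complete under a separate SAP. The adjusted result belongs in the final analysis as support.

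**What to change.** Before unblinding for the final analysis, amend SAP 7.1, 10, 14.1.3 and 14.2.3 as follows.

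- Keep the unadjusted log-rank as the governing test, and say so.
- For the primary and secondary endpoints, pre-specify one supportive Cox model and one stratified log-rank using screening TB antigen minus Nil in fixed categories: <0.10, 0.10 to <0.20, and 0.20 to <0.35 IU/mL. Categories avoid taking the log of zero or negative differences. A participant who is negative only under the 25%-of-Nil rule, with a difference of 0.35 or more, should go in the top category.
- Use the screening value and not Day 84, which follows vaccination.
- Tabulate screening TB antigen minus Nil by arm for the Safety and modified intent-to-treat sets.

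The cost is SAP wording, one model term and one table row; no new data are needed. The downside is that adjusted and unadjusted estimates appear side by side, which the stated precedence resolves.

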### 5.3. MODIFIED INTENT-TO-TREAT ANALYSIS SET

The Modified Intent-to-treat analysis set is defined as all participants included in the Safety analysis set who had a negative QFT-GIT test result at Day 84.

A participant will be programmatically included in the Modified Intent-to-treat analysis set if the participant:

- Is included in the Safety analysis set.
- AND
- Has a negative QFT-GIT test result at the Day 84 visit.

For analyses and presentations based on the Modified Intent-to-treat analysis set, participants will be analyzed according to the treatment assigned regardless of the treatment received.

The Modified Intent-to-treat analysis set will be used for efficacy analyses.

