  - o As a sensitivity analysis the content of this table will be repeated in a separate table using interval censoring for the MITT analysis set.
- First QFT-GIT conversion by visit:
  - o Number and percentage (%) of participants with first QFT-GIT conversion at each of the scheduled visits.
  - o Number of participants at risk for first conversion at each scheduled visit.
  - o At risk defined as participants with:
    - A negative QFT-GIT result at the preceding visit without a previous positive QFT-GIT result.
    - A QFT-GIT result available at the relevant visit.
  - o This table will be repeated for the Per Protocol analysis set.
- Follow-up time until first QFT-GIT conversion:
  - o Number of participants contributing to the total follow-up time (at risk).
  - o Cumulative number of participants:
    - Censored (not due to a primary endpoint at the time of the last available non-positive QFT-GIT result).
    - With an event (primary endpoint).
  - o The total follow-up time (person-months), as measured from Randomization (1 month = 4 weeks).
  - o The Kaplan-Meier event rate presented at each relevant post-Day 84 visit.
  - o This table will be repeated for the Per Protocol analysis set.

Document: Aeras\_C-040-404\_SAP\_V2\_0

Author: [name]

Version Number:

2.0

Version Date:

29SEP2017

Template No: CS\_TP\_BS016 – Revision 3

Reference: CS\_WI\_BS005

Effective Date: 01May2012

Copyright © 2012 Quintiles Transnational Corp. All rights reserved.

The contents of this document are confidential and proprietary to Quintiles Transnational Corp. Unauthorized use, disclosure or reproduction is strictly prohibited.

- Primary endpoints by school/region:
  - o Number and percentage (%) of participants who experienced a primary endpoint in each school/region.
- Primary endpoints by site and sex:
  - o Number and percentage (%) of participants who experienced a primary endpoint in each site/sex.

The following table will be presented for the Randomized analysis set:

- QFT-GIT conversion rates including all post-Day 0 conversions:
  - o Number and percentage (%) of participants in each conversion status category:
    - Yes.
    - No.
    - Missing.
  - o Two groups of conversion time points included:
    - Any QFT-GIT conversion (early [Day 84] or post-Day 84) (at risk participants include all participants).
    - Early (Day 84) conversion (at risk participants include all participants).
  - o Hazard ratio (H4:IC31/comparator) presented:

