    - Point estimates (based on the Cox regression model).
    - P-values for the comparison of the estimated hazard ratios of QFT-GIT conversion based on a one-sided log-rank test.
      - H4:IC31 versus Placebo.
      - BCG versus Placebo.
      - H4:IC31 versus BCG (included at the request of the sponsor's partner).
  - o Vaccine efficacy presented:
    - Point estimate (based on the hazard ratio estimates).
    - 80% two-sided CI based on the hazard ratio estimate from the Cox regression model.

The following figures will be presented for the Modified Intent-to-treat analysis set:

- Time on study:
  - o Kaplan-Meier plot per treatment group.
  - o Cumulative follow-up time as measured from randomization (1 month = 4 weeks).
  - o Event is defined as whichever occurs first:
    - Initial QFT-GIT conversion.
    - Early termination/study completion.
  - o This figure will be repeated for the Per Protocol analysis set.
- Time to first post-Day 84 QFT-GIT conversion, primary endpoint:
  - o Kaplan-Meier plots per treatment group for the following:
    - Time to first post-Day 84 QFT-GIT conversion.
  - o Time to first QFT-GIT conversion will be presented in months, measured from Day 84 (1 month = 4 weeks).
    - Censored (at the time of the last available non-positive QFT-GIT result).
  - o This figure will be repeated for the Per Protocol analysis set.
- Time to first post-Day 84 QFT-GIT conversion (interval-censored sensitivity analysis):
  - o Survival function estimate plot per treatment group based on a life-table analysis.
  - o Time to QFT-GIT conversion measured from Day 84.
  - o Time to conversion will be presented in 6-month intervals.

---

Document: Aeras\_C-040-404\_SAP\_V2\_0

Author: [name]

Version Number:

2.0

Version Date:

29SEP2017

Template No: CS\_TP\_BS016 – Revision 3

Reference: CS\_WI\_BS005

Effective Date: 01May2012

Copyright © 2012 Quintiles Transnational Corp. All rights reserved.

The contents of this document are confidential and proprietary to Quintiles Transnational Corp. Unauthorized use, disclosure or reproduction is strictly prohibited.

The following figure will be presented for the Randomized analysis set:

- Time to First QFT-GIT Conversion (Early or Post-Day 84):
  - o Kaplan-Meier plots per treatment group for the following:
    - Time to any QFT-GIT conversion (early or post-Day 84) measured from Day 0.

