### 14.1.3. DERIVATIONS

Based on the aforementioned, the following variables, as presented in the planned TLF shells, will be derived for post-vaccination visits and/or time points:

- QFT-GIT testing compliance derived per visit:
  - o Yes: QFT-GIT assessment date is within the protocol-defined visit window.
  - o No: QFT-GIT assessment date is outside the protocol-defined visit window.
  - o Missing: The participant is expected to have a QFT-GIT assessment available.
  - o Refer to APPENDIX 8: Protocol-defined Visit Windows for the relevant protocol-defined visit windows.
- QFT-GIT result classification at each visit (use the retest result if available). The Investigator's assessment will be used, which is based on the algorithm below.

QFT-GIT Result Classification	QFT Nil	QFT Ag - QFT Nil	QFT Mitogen - QFT Nil
Positive	≤ 8.0	≥ 0.35 (primary analysis threshold) and ≥ 25% of QFT Nil value	Any
Negative		< 0.35 (primary	≥0.5

Document: Aeras\_C-040-404\_SAP\_V2\_0

Author: [name]

Version Number:

2.0

Version Date:

29SEP2017

Template No: CS\_TP\_BS016 – Revision 3

Reference: CS\_WI\_BS005

Effective Date: 01May2012

Copyright © 2012 Quintiles Transnational Corp. All rights reserved.

The contents of this document are confidential and proprietary to Quintiles Transnational Corp. Unauthorized use, disclosure or reproduction is strictly prohibited.

QFT-GIT Result Classification	QFT Nil	QFT Ag - QFT Nil	QFT Mitogen - QFT Nil
Indeterminate		analysis threshold) OR ≥ 0.35 (primary analysis threshold) and < 25% of QFT Nil value	< 0.5
Indeterminate	> 8.0	Any	Any

- If the QFT-GIT result is indeterminate at any of the visits Day 84, M6, M9, M12, M15, M18, M21, M24, M27 or M30, the QFT-GIT test will be repeated (QUANT2 form in the eCRF used to record the result). If the repeat result is negative or indeterminate, the participant will continue with the study visits as if the participant did not convert, and the result for the corresponding visit will be deemed “negative”.
- Any QFT-GIT conversion status:
  - o The QFT-GIT conversion status is assigned hierarchically in the order provided below:
    - Yes: Participant has at least one positive QFT-GIT result classification, regardless of missing or indeterminate results at any other visit and regardless of at which visit the positive QFT-GIT result is recorded.

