      - Post-Day 84 QFT-GIT conversion: First positive QFT-GIT result classification recorded post-Day 84.
      - Early QFT-GIT conversion: First positive QFT-GIT result classification recorded at Day 84.
    - No: Participant has no positive QFT-GIT result classification and the last available QFT-GIT result classification is negative.
    - Missing: Participant has no positive/negative/indeterminate QFT-GIT result classification available.
- Censored:
  - o Participants who do not experience a primary endpoint or early conversion (early conversion is only applicable to the analyses based on the Randomized analysis set), will be censored at the date of their last available, non-positive QFT-GIT result.
  - o The following SAS code will be implemented for all Kaplan-Meier analyses, where:
 

```
PROC LIFETEST DATA = <>;
    TIME Months*Censored(1);
    TEST Treatment_Group;
RUN;
```

    - Censored = 1 represents censored participant.
    - Censored = 0 represents participant who experienced an event.
    - Months represent the available follow-up time (months) per participant since:
      - Day 84 (applicable to analyses based on the mITT and PP analysis set).
      - Randomization (applicable to analyses based on the Randomized analysis set).
- Event:
  - o Participants who experience a primary endpoint or early conversion will be indicated as having an event (depending on the relevant table, early converters will be included/excluded from the participants experiencing an event).

Document: Aeras\_C-040-404\_SAP\_V2\_0

Author: [name]

Version Number:

2.0

Version Date:

29SEP2017

Template No: CS\_TP\_BS016 – Revision 3

Reference: CS\_WI\_BS005

Effective Date: 01May2012

Copyright © 2012 Quintiles Transnational Corp. All rights reserved.

The contents of this document are confidential and proprietary to Quintiles Transnational Corp. Unauthorized use, disclosure or reproduction is strictly prohibited.

- Available follow-up time (months) until first QFT-GIT conversion:
  - o The number of months of follow-up time will be derived for each participant based on the date of randomization/Day 84 (depending on the relevant table) and either the censor or event date.
  - o 1 month = 4 weeks.
  - o For the sensitivity analysis the follow-up time will be rounded to the nearest 6-month interval for any of the following visits:
    - Month 6.
    - Month 12
    - Month 18.
    - Month 24.

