### 14.2.2. ANALYSIS OF SECONDARY EFFICACY ENDPOINT

The following table will be presented for the Modified Intent-to-treat analysis set:

- QFT-GIT 6-month sustained conversion rates:
  - o Number and percentage (%) of participants in each conversion status category:
    - Yes.
    - No.
    - Missing.
  - o Hazard ratio (H4:IC31/comparator) presented:
    - Point estimates (based on the Cox regression model).
    - P-values for the comparison of the estimated hazard ratios of QFT-GIT 6-month sustained conversion based on a one-sided log-rank test.
      - H4:IC31 versus Placebo.
      - BCG versus Placebo.
      - H4:IC31 versus BCG (at the request of the sponsor's partner).
  - o Vaccine efficacy presented:
    - Point estimate (based on the hazard ratio estimate).
    - 80% two-sided CI based on the hazard ratio estimate from the Cox regression model.
  - o This table will be repeated for the alternative threshold value.
  - o These tables (based on the original threshold as well as the alternative threshold) will be repeated for the Per Protocol analysis set. This table (based on the original threshold) will also be repeated for the Adjusted Modified Intent-to-treat (First Recall Positive Omit) analysis set and the adjudication approach (refer to Section 3.3: Changes to Analysis from Protocol).
  - o As a sensitivity analysis both of these tables (original threshold and the alternative threshold outputs) will be repeated in separate tables using interval censoring for the MITT analysis set.

---

Document: Aeras\_C-040-404\_SAP\_V2\_0

Author: [name]

Version Number:

2.0

Version Date:

29SEP2017

Template No: CS\_TP\_BS016 – Revision 3

Reference: CS\_WI\_BS005

Effective Date: 01May2012

Copyright © 2012 Quintiles Transnational Corp. All rights reserved.

The contents of this document are confidential and proprietary to Quintiles Transnational Corp. Unauthorized use, disclosure or reproduction is strictly prohibited.

The following figures will be presented for the Modified Intent-to-treat analysis set:

- Time to 6-month sustained QuantiFERON conversion:
  - o Kaplan-Meier plots per treatment group for the following:
    - Time to first of three consecutive post-Day 84 QFT-GIT positive results.
  - o Time to sustained QFT-GIT conversion will be presented in months, measured from Day 84 (1 month = 4 weeks) to the date of the first of three consecutively positive QFT-GIT results.

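### The interval-censored sensitivity analysis takes its left bound from the preceding scheduled test even when that test was missed, and its life-table rounding rule splits or displaces conversions

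*SAP*

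**What the plan says.** The primary hazard ratio and efficacy table is repeated under interval censoring for the mITT set (SAP 14.1.2). SAP 14.1.3 gives the bounds: "Left and right censoring values are dependent on where the event is identified". There is one pair per detection visit: Month 6 (3,6), Month 12 (6,12), Month 18 (12,18), Month 24 (18,24). There is no row for a missed preceding test. The same section counts a participant as converted "regardless of missing or indeterminate results at any other visit". SAP 7.3 imputes no missing data. The only deemed-negative rule covers a repeat test that is again indeterminate.

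Two other rules bear on this. The mITT set requires that a participant "Has a negative QFT-GIT test result at the Day 84 visit" (SAP 5.3). The by-visit conversion table counts a participant as at risk only with "A negative QFT-GIT result at the preceding visit without a previous positive QFT-GIT result" (SAP 14.1.2).

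The companion figure is a life-table plot with "Time to QFT-GIT conversion measured from Day 84" (SAP 14.1.2). SAP 14.1.3 adds: "For the sensitivity analysis the follow-up time will be rounded to the nearest 6-month interval for any of the following visits", namely Months 6, 12, 18 and 24, with a month of four weeks. The code has "METHOD=lt INTERVALS=(0 to 2 by 0.5" in years. The SAP says neither whether rounding applies to elapsed time or to the visit label, nor which end of an interval is included.

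SAP 14.2.2 says that the secondary tables, at both thresholds, "will be repeated in separate tables using interval censoring for the MITT analysis set". SAP 14.2.3 gives no bounds of its own.

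**The concern.** An interval-censored analysis is run to claim no more about timing than the tests show. The left bound should be the last test that was actually negative. A bound fixed by the schedule asserts a negative result that was never observed whenever the preceding test was missed.

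The figure has a separate problem. If the rounding step conflicts with the schedule, the plotted curve reflects visit timing or labelling rather than the conversions found by each visit. At stake are the inputs to the interval-censored tables and the reading of one descriptive figure.

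**Working it through.** **The bounds table.** Visit days divided by 28: 84/28 = 3, 168/28 = 6, 336/28 = 12, 504/28 = 18, 672/28 = 24. The SAP's pairs are therefore consecutive scheduled visits, counted from Day 0.

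**With the preceding test missed.** Month 12 after a missed Month 6: the SAP gives (6,12), the tests support (3,12). Month 18 after a missed Month 12: (12,18) against (6,18). Month 24 after a missed Month 18: (18,24) against (12,24). The Month 6 row is always right, because mITT entry needs a negative Day 84 test.

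**Share of events affected.** Inputs: 10% per year endpoint rate and 7% per year loss (protocol 7.6), treated as constant hazards from Day 84; each test missed independently with probability m = 5% or 10% (assumed). Cumulative conversion is 1 − exp(−0.10 × days since Day 84 / 365.25):

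- Month 6: 84 days, 2.27%
- Month 12: 252 days, 6.67%
- Month 18: 420 days, 10.86%
- Month 24: 588 days, 14.87%

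The first two increments are p1 = 0.0227 and p2 = 0.0667 − 0.0227 = 0.0440. Among events found at Month 12, the share with Month 6 missed is m(p1 + p2)/(p2 + m·p1):

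- m = 5%: 0.05 × 0.0667/(0.0440 + 0.0011) = 7.4%
- m = 10%: 0.10 × 0.0667/(0.0440 + 0.0023) = 14.4%

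The same reasoning gives about 10% and 19% at Months 18 and 24, and 0% at Month 6. Over all visits, with loss, the share is 7.6% and 14.9%. With an assumed 310 per arm negative at Day 84 and a hazard ratio between 0.5 and 1, one vaccine-placebo comparison followed to Month 24 has roughly 64 to 85 events, so about 5 to 6, or 9 to 12, are affected.

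**Effect on the estimates.** I compared a piecewise-constant interval-censored proportional-hazards fit under the SAP bounds with one using (last negative, first positive).

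- Four pieces, true HR 0.5, 5% or 10% missed in both arms: HR 0.500 either way.
- Four pieces, true HR 0.5, 5% against 25% missed: efficacy 49.9% or 50.3%, depending on which arm misses more, instead of 50.0%.
- SAP 14.1.3 leaves the number of pieces open. For 1, 2 or 4 pieces in large samples, the HR differs by at most 0.0008 with 10% missed in both arms (true HR 0.5) and 0.0017 with 5% against 10% (true HR 1.0).
- At 310 per arm (four pieces, 300 runs in each of 8 scenarios), the mean difference is at most 0.0004 and the largest is 0.008.
- The fitted baseline hazard moves later. With 10% missed it is 0.090, 0.095, 0.101 and 0.111 per year over the four intervals, against a true 0.10 in each.

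**The life-table figure.** From Day 84, scheduled tests fall at (168−84)/28 = 3, (336−84)/28 = 9, (504−84)/28 = 15 and (672−84)/28 = 21 months. Each is exactly halfway between multiples of 6. A Month 6 test one day early rounds to 0 and one day late rounds to 6. With dates spread over the SAP Appendix 8 windows, just under half round down.

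If the rule means visit labels, the times are 0.5, 1, 1.5 and 2 years. With intervals that include their lower limit (the SAS convention, assumed), these fall in [0.5,1), [1,1.5), [1.5,2) and 2 or later.

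Cumulative conversion with no missed tests, at the protocol rates:

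| | 0.5 y / M6 | 1 y / M12 | 1.5 y / M18 | 2 y / M24 |
|---|---|---|---|---|
| Detected by the visit | 2.3% | 6.7% | 10.9% | 14.9% |
| Rounded time from Day 84 (approximate; depends on visit dates) | 1.1% | 4.5% | 8.8% | 14.2% |
| Visit labels, lower limit included | 0% | 2.3% | 6.8% | 11.0% |

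In the last row the Month 24 conversions, 26% of all, fall outside the last closed interval.

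**The case against.** The strongest reply is that no planned result changes. The tables report HR, p-values, efficacy and confidence intervals. The HR and efficacy shift far less than their sampling error, and no output reports the baseline hazard. That stands. A reader might infer that the robustness check on efficacy is invalid or biased; the calculations do not support this, even with unequal missingness.

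Second, a reader might infer that the figure misplaces every conversion however the rule is read. It does not. Under rounding from Day 84, conversions that round down land in the interval containing their detection time (lower limit included), so the fault is a split. Under visit labels, the one-interval delay depends on a convention the SAP does not state. If intervals included their upper limit, labels would be right on a Day 0 scale, although SAP 14.1.2 measures this figure from Day 84.

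Third, the by-visit at-risk rule belongs to a descriptive count, and different outputs may use different denominators. It shows that the SAP can require an observed negative; it is not a contradiction.

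Fourth, the missed-test rate is assumed, and protocol 3.6.4 asks for missed procedures to be rescheduled when possible, so the true share may be lower. Conversion by visit and Kaplan-Meier rates are also planned elsewhere in SAP 14.1.2.

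What remains is a stated rule that enters an unobserved negative, and a rounding step that conflicts with the test schedule.

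**Conclusion.** The point holds as a minor one. As written, the bounds are wrong for any Month 12, 18 or 24 conversion that follows a missed test: about 8% or 15% of events at an assumed 5% or 10% missed. The rounding rule distorts the life-table curve, by splitting conversions at the midpoints under one reading, or by a one-interval delay under the other if lower limits are included.

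The reach is the interval-censored tables and one descriptive figure. For the secondary tables, use of the same bounds is an inference, because SAP 14.2.3 gives none. HR and efficacy are essentially unchanged, and the primary Cox and log-rank results are untouched. The sizes rest on the protocol's event and loss rates, independent missed tests, and visit dates spread across the permitted windows.

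**What to change.** In SAP 14.1.3, replace the bounds table with: left = last observed negative QFT-GIT, right = first positive, by nominal visit. State the same rule for the secondary interval-censored tables, with right = the first of the three consecutive positives and left = the last test not meeting the conversion threshold in use. That wording also covers results between 0.2 and 0.70 IU/mL under the alternative threshold.

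Drop the rounding. Plot cumulative conversion at nominal Months 6, 12, 18 and 24, with each conversion in the interval ending at its detection visit. Keep non-converters fully at risk through their last negative visit and remove them afterwards. With no missed tests and the protocol rates this returns 2.3%, 6.7%, 10.9% and 14.9%. The censoring rule must be written down: with the usual life-table adjustment (number at risk less half the censored), the last point is about 18.7% if Month 24 negatives share the final interval, and about 14.7% if each participant's last negative is moved to the next interval. A nonparametric interval-censored (Turnbull) estimate from the corrected bounds is an acceptable alternative.

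The cost is SAP wording and one derivation. Sample collection dates are already recorded (SAP 14.1.2), and no new data are needed.
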